## **6.7 Safety Endpoint Analyses**

### **6.7.1 Treatment Emergent Adverse Events**

Only TEAEs will be summarized. The non-treatment emergent AEs are included in medical history summaries. Note that all TEAEs recorded in the eCRFs will be included in the safety analysis, even if they are outside the collection window.

The following TEAEs will be provided in summary tables as well as displayed in listings:

- Any TEAEs
- Treatment-related TEAEs
- TEAEs by CTCAE severity Grade  $\geq 3$
- Treatment-related TEAEs with CTCAE severity Grade  $\geq 3$
- TEAEs related to each individual study drug
- Any SAEs
- Treatment-related SAEs
- SAEs related to each individual drug
- Fatal AEs
- AESIs
- IREs
- TEAEs that result in study discontinuation
- TEAEs that lead to interruption of each individual drug
- TEAEs that lead to withdrawal of each individual study drug

All of these summaries will display the number and percent of patients who experience the given event and will display events by System/Organ/Class (SOC) and Preferred Term (PT). Events will be displayed alphabetically for SOC and in descending order of overall PT incidence within each SOC.

In addition, an overall summary table will be generated to display the number and percent of patients who experience at least one event of each of above TEAE types.

### **6.7.2 Laboratory Values**

Summaries of laboratory values will display descriptive statistics for numerically quantified labs. Summaries will be grouped by lab panel (hematology, blood chemistry, and urinalysis) and will be displayed by visit for each lab parameter. Graphs of mean values over time may also be generated.

In cases where an abnormality resulted in a repeat lab test, the repeat value will be used for the summaries.

Shift tables will be used to display the percent of patients who have a shift in post-baseline maximum CTCAE grade from baseline for each lab parameter.

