- Any Grade 3 elevation of one or more transaminases $> 5.0 - 8.0 \times$ ULN that does not resolve to Grade 2 (i.e., $> 2.5 - 5.0 \times$ ULN) within 7 days and Grade 1 (i.e., $> ULN - 2.5 \times$ ULN) within 14 days. In addition, steroids must be tapered to ≤ 10 mg of prednisone or equivalent per day, by Day 14. Please see [Section 6.5.2.2](#) for further management guidelines.
- A Grade 3 elevation of total bilirubin that is $> 5 \times$ ULN, irrespective of duration.
- Any Grade 3 elevation of total bilirubin $> 3.0-5.0 \times$ ULN that does not resolve to Grade 2 (i.e., $> 1.5-3.0 \times$ ULN) within 7 days and Grade 1 (i.e., $> ULN-1.5 \times$ ULN) within 14 days. In addition, steroids must be tapered to ≤ 10 mg of prednisone or equivalent per day, by Day 14. Please see [Section 6.5.2.2](#) for further management guidelines.
- Any event meeting the criteria for Hy's law as follows (all three features):
 - Aspartate aminotransferase (AST) and/or alanine aminotransferase (ALT) $> 3 \times$ ULN.

- Concurrent elevation of total bilirubin $> 2 \times$ ULN without initial evidence of cholestasis (e.g., elevated serum alkaline phosphatase [ALK-P]).
- No alternative etiology can be identified.

Dose Escalation Rules

The **Dose Escalation Phase (Part A)** of this trial will proceed using a conventional 3 + 3 approach, and will begin with enrollment of 3 patients at a dose of 200 mg pembrolizumab administered as an IV infusion once every 3 weeks and an initial dose of 10 mg/kg margetuximab administered as an IV infusion once every 3 weeks. Successive dose escalation cohorts will be enrolled as outlined below. The MTD or MAD will be determined based on the assessment of DLTs during the DLT evaluation period. Patients who are not evaluable for safety for the full DLT evaluation period for reasons other than study drug-related toxicity will be replaced in the same dose-level cohort.

- If 0 of the first 3 patients treated at a given dose level experience a drug-related DLT during the DLT evaluation period, the dose will be escalated and 3 patients will be enrolled and treated at the next higher dose level.
- If 1 of the first 3 patients treated at a given margetuximab dose level experiences a drug-related DLT, then 3 additional patients will be enrolled at that dose level (thus making a total of 6 patients in this cohort) to further assess the safety of the combination.

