6.5.2.2 Hepatic Toxicity

6.5.2.2.1 Elevations in Transaminases

Management guidelines for patients experiencing hepatic toxicity are as follows:

- Grade 1 elevations
 - No specific therapy required
- Grade 2 elevations
 - For elevations in transaminases 3 to 5 \times ULN (Grade 2), rule out viral and other etiologies, and consider immediate oral steroids such as prednisone 60 mg/day divided twice daily, and hold pembrolizumab and margetuximab.
 - If improvement to \leq Grade 1 does not occur within 48 hours with oral steroids, consider IV steroids such as methylprednisolone at 2 mg/kg/day divided twice daily or oral steroids such as prednisone 60 to 120 mg per day, divided twice daily

- Resume pembrolizumab and margetuximab at the next scheduled dose if:
 - No more than one dose of pembrolizumab and margetuximab was missed
- If improvement to \leq Grade 1 does not occur within 14 days, discontinue pembrolizumab and margetuximab.
- Grade 3 elevations
 - Discontinue pembrolizumab and margetuximab
 - Initiate IV steroids and,
 - If no response to corticosteroid therapy within 3 to 5 days is observed, consider adding immune suppression therapy with mycophenolate. Do not use infliximab in these cases because of a potential for autoimmune hepatitis (40).
 - Monitor liver function tests at least twice weekly (or more frequently as clinically appropriate in the judgment of the investigator) until transaminases have returned to Grade 1 or baseline.
- Grade 4 elevation
 - Discontinue pembrolizumab and margetuximab
 - Treat as for Grade 3 elevation.

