## **6 STATISTICAL METHODOLOGY**

### **6.1 General Considerations**

This Phase 1b/2 study is primarily observational and, thus, the majority of the statistical summaries will be descriptive. Safety and efficacy summaries will be provided for each dose level cohort and for all dose level cohorts combined. Response rates will be calculated for the response evaluable population.

Unless otherwise specified, the following general considerations are applied in data analyses:

- The baseline value is defined as the latest value prior to the start of study drugs.
- Categorical data will be summarized by the number and percent of patients falling within each category.
- Continuous variables will be summarized by descriptive statistics, including mean, standard deviation, median, minimum, and maximum.
- Time-to-event endpoints will be summarized by the number and percent of the event, median time and corresponding 95% confidence interval (CI), and event free rate and corresponding 95% CI at the specified time points of interest.
- All data summaries and tabulations will be conducted using SAS® software Version 9.3 or higher.

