### **6.2 Missing Data**

Data that are reported as missing will be treated as missing in all data summaries. Incomplete dates will be imputed and defined in the Statistical Programming Plan (SPP). In descriptive summaries for safety, observations that are spurious (extreme relative to the majority of the data) will not be altered or removed from the summary.

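### SAP 6.7.2 puts the repeat in place of an abnormal lab value without requiring a documented error, so valid abnormal results can drop out of the by-visit lab summaries

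*SAP*

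**What the plan says.** SAP 6.7.2 plans descriptive statistics for each lab parameter by visit, with optional plots of means over time. It then states: "In cases where an abnormality resulted in a repeat lab test, the repeat value will be used for the summaries". The next paragraph adds: "Shift tables will be used to display the percent of patients who have a shift in post-baseline maximum CTCAE grade from baseline". It does not say whether the repeat rule also governs that table.

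SAP 6.1 fixes which statistics are shown: "Continuous variables will be summarized by descriptive statistics, including mean, standard deviation, median, minimum, and maximum". It also defines baseline: "The baseline value is defined as the latest value prior to the start of study drugs".

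SAP 6.2 says that, in descriptive safety summaries, "observations that are spurious (extreme relative to the majority of the data) will not be altered or removed from the summary". Protocol 9.1 makes the same commitment.

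Protocol 7.9.5.1 (Changes in Clinical Laboratory Parameters) allows the investigator to repeat a test, or order others, in order to check a first result. Laboratory error is mentioned there only in connection with AE reporting. Protocol 9.4.2 promises a list showing both original and repeat values and contains no replacement rule.

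**The concern.** Under SAP 6.7.2 the original value leaves the summary because it was abnormal and was retested, not because it was wrong. A repeat done to check a result may confirm it. The original is then a valid observation, and the rule still sets it aside. The SAP states no matching rule for normal originals, so the selection works on abnormal values only.

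Safety is a primary objective. The maximum, minimum and SD of a lab parameter at a visit are where a single marked abnormality would show, and these are the statistics the rule affects most. Lower-grade abnormalities are the most exposed: protocol 7.9.5.1 generally does not require Grade 1 findings to be reported as AEs and leaves Grade 2 findings to judgement, so for many of them the lab tables are the only tabulated summary.

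**Working it through.** The documents state no figure for this rule, so there is nothing to reproduce. They give no lab distributions, repeat rate or repeat timing, so the numbers below illustrate the mechanism and do not estimate its size.

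**1. The rules side by side.** SAP 6.2 and protocol 9.1: an extreme safety value is neither altered nor removed. SAP 6.7.2: an abnormal value that was repeated is replaced. When the replaced value is extreme relative to the rest, both cannot be followed. Protocol 7.9.5.1 shows that a repeat need not mean an error, so SAP 6.7.2 cannot be read as covering errors only.

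**2. One replacement at one visit.** Assumed: n = 30 (one Part B region, all with a value at the visit), 29 patients at 0.8 x ULN and one at 6.0 x ULN, replaced by a repeat of 1.5 x ULN. With one value lying d above n − 1 equal values, mean = 0.8 + d/n and sample SD = d/√n.

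| | Original kept (d = 5.2) | Repeat used (d = 0.7) |
|---|---|---|
| Mean | 0.8 + 5.2/30 = 0.973 | 0.8 + 0.7/30 = 0.823 |
| SD | 5.2/√30 = 0.949 | 0.7/√30 = 0.128 |
| Median | 0.8 | 0.8 |
| Maximum | 6.0 | 1.5 |

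The mean moves by (6.0 − 1.5)/30 = 0.15 x ULN. Because the shift is the gap divided by n, it is larger in a small cohort: the same swap among 6 patients gives 4.5/6 = 0.75 x ULN.

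**3. Average effect on a mean.** Assumed: original X and repeat Y are standard bivariate normal with correlation ρ, a share p of originals lies above the abnormality limit c, and a share f of those is repeated. Then the shift in the mean is −f(1 − ρ)φ(c), in SD units.

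- For p = 10%, c = 1.282 and φ(c) = 0.1755. With ρ = 0.7 and f = 1 the shift is −0.3 × 0.1755 = −0.053 SD.
- Across p = 5–20%, ρ = 0.5–0.9 and f = 0.5–1 it runs from −0.005 to −0.14 SD.

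This one-sided model covers regression to the mean only. A repeat can be worse than the original, and for parameters that go abnormal in both directions the mean shifts may partly cancel.

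**4. Maximum-grade shift table.** If the rule applies there, the grades used are a subset of all valid post-baseline grades. The maximum of a subset cannot exceed the maximum of the whole set, so a patient's maximum grade can only fall or stay the same. If the rule does not apply there, this table is unaffected.

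**The case against.** The strongest reply is that little depends on these statistics. The study is single-arm and descriptive; DLTs and AEs carry the safety assessment, and ORR carries futility. AE tables do not use the rule, Grade 3 and 4 lab findings should be reported as AEs or SAEs under protocol 7.9.5.1, and the protocol 9.4.2 list keeps every original beside its repeat. The sentence in SAP 6.7.2 follows the by-visit paragraph and precedes the shift-table paragraph, so it may never have been meant to reach the shift tables. A window or selection convention may sit in the separate statistical programming plan (SAP 7), which is not among the documents. All of this stands, and it limits the severity.

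It can also be said that SAP 6.2 forbids dropping values for being extreme, while SAP 6.7.2 is a specific rule for choosing between two measurements. That narrows the conflict to cases where the replaced value is extreme, but does not remove it.

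A reader might infer more from protocol 6.5.2.2.1, which says of Grade 3 transaminase elevations "Monitor liver function tests at least twice weekly" and continues "until transaminases have returned to Grade 1 or baseline". On that view a whole series ending in recovery would count as repeats, and a recovered value would replace the peak. The documents do not support this. The section calls these tests monitoring, not repeats; they come after an instruction to discontinue both drugs; and nothing assigns a later recovery value to the visit of the original.

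Nor is it a defect in itself that an AE table and a by-visit lab table differ: one counts patients over the reporting period, the other describes a visit.

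**Conclusion.** The point holds as a minor one. As written, SAP 6.7.2 replaces valid abnormal values in the by-visit lab statistics without an error condition, and this is inconsistent with SAP 6.2 and protocol 9.1 when the replaced value is extreme. Movement toward normal is the expected direction, not a certainty.

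The size is unknown. Under the assumptions shown, effects on means are probably small in groups of expansion-cohort size, while the maximum and SD at a visit can change greatly through a single replacement. Reach into the maximum-grade shift table is possible but not stated.

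The documents do not support the reading that abnormal results are lost from the study: the AE tables and the protocol 9.4.2 list are untouched. No efficacy or dose-finding conclusion depends on this rule.

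**What to change.** Replace the sentence in SAP 6.7.2 with:

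> Post-baseline by-visit summaries use the original (first valid) scheduled value for that visit; a repeat replaces it only when a sample or assay error in the original is documented. All valid post-baseline values, original and repeat, scheduled and unscheduled, enter the maximum-CTCAE-grade shift tables. Baseline remains as defined in SAP 6.1. Original and repeat values are listed as in protocol 9.4.2.

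Naming the first valid scheduled value matters. A looser rule of one pre-specified value per visit would still permit taking the last one, and since repeats follow abnormal results, that would bring the same selection back.

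The cost is one short SAP paragraph and no new data collection. The downside is that reported lab abnormalities may be slightly higher.

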### **6.7.3 Other Safety Endpoints**

#### **6.7.3.1 ECG and MUGA Scan**

ECGs will be collected and analyzed for evidence of cardiac toxicity, especially prolongation of QT interval. The following categories for QTcF interval and maximum post dose change from baseline QTcF interval ( $\Delta$ QTcF) will be used in summary and shift tables:

QTcF:  $\leq 450$  msec,  $>450$  to 480 msec,  $>480$  to 500 msec, and  $>500$  msec

$\Delta$ QTcF:  $\leq 30$  msec,  $>30$  to 60 msec, and  $>60$  msec

MUGA scan or echocardiogram will be presented by change from baseline in LVEF.

#### **6.7.3.2 Physical Exams and Vital Signs**

Physical exams and vital signs may be summarized with descriptive statistics at each visit and time point where they are collected. The following categories will be used in shift tables for vital signs.

- Systolic blood pressure (mmHg):  $<90$  (Low), 90-120 (Normal),  $>120$  (High)
- Diastolic blood pressure (mmHg):  $<60$  (Low), 60-80 (Normal),  $>80$  (High)
- Heart rate (Beats/min):  $<60$  (Low), 60-100 (Normal),  $>100$  (High)
- Respiratory Rate (Breaths/min):  $<12$  (Low), 12-18 (Normal),  $>18$  (High)
- Temperature ( $^{\circ}$ F):  $<97.8$  (Low), 97.8-99.1 (Normal),  $>99.1$  (High)

### **6.8 Pharmacokinetic, Pharmacodynamic, and Immunological Parameter Endpoint Analyses**

**Pharmacokinetic Analysis:** Summary statistics will be tabulated for PK parameters by margetuximab dose. Geometric means and percent coefficients of variation will be reported for  $C_{\max}$ ,  $AUC_{\tau}$ , and  $C_{\text{trough}}$ ; arithmetic means and standard deviations will be reported for terminal half-life ( $T_{\text{half}}$ ), CL, and  $V_{\text{ss}}$ ; and medians, minimum, and maximum will be reported for  $T_{\max}$ . Separate scatter plots of  $C_{\max}$  and AUC will be provided versus dose to assess dose dependency. Population PK analyses may be conducted using data from this study alone or combined with data from other studies.

**Immunogenicity Analysis:** The proportion of patients who are negative for margetuximab ADA at baseline and become positive in this assay, the proportion of patients who are negative at baseline and remain negative, and those who have positive ADA at baseline that increases or decreases in titer over the course of treatment will be summarized.

**Pharmacodynamic Analysis:** Summary statistics for pharmacodynamics parameters such as, but not limited to, those listed under section, “Pharmacodynamics/Biomarkers/Tumor Biopsy” of the protocol and corresponding changes from baseline, will be summarized and/or may also be presented graphically as well. Possible associations between changes in pharmacodynamics measures of interest and margetuximab dose and exposure may be explored.

## **6.9 Futility Analysis**

During expansion phase, an futility analysis of ORR will be performed after 15 patients in each region (North America and Asia) have been enrolled and each patient received at least one post baseline tumor assessment. Duration of response for responders as well as tumor size change over time for all 15 patients per region may also be calculated in assisting interim decision making.

## **6.10 Subgroup Analysis**

Efficacy analyses will be performed by race (Asian vs Non-Asian), tumor location (GC vs GEJ), and other demographics and baseline characteristics. The analyses will also be performed by baseline biomarkers such as HER2 IHC status (IHC3+ vs IHC2+), PD-L1 status (PD-L1+ vs PD-L1-), double positive status (HER2 IHC3+ and PD-L1+ vs others), and by alleles coding for CD16A (VV, FF, FV, and FF and FV combined [F Carrier]), respectively.

## **7 LIST OF TABLES, LISTINGS, AND FIGURES**

The list of tables, listings, and figures (TLFs) and associated shells planned for the clinical study report based on the analyses described in this SAP will be provided in a separate statistical programming plan (SPP), which will also include data reporting conventions and programming specifications for the development of these TLFs.

